8.8.9 Protocol Deviations

The principal investigator will not deviate from the protocol without obtaining approval from the IRB or Ethics Committee and the sponsor. In medical emergencies, the investigator will use medical judgment and will remove the subject from immediate hazard, then notify the sponsor, and the IRB or Ethics Committee immediately regarding the type of emergency and course of action taken. Any action in this regard will be recorded on the appropriate CRF.

9 SCHEDULE OF PROCEDURES

The study comprises of 6 periods: screening, run-in (for subjects in groups 2, 3, and 4), onset and maintenance, offset, and end of study. The trial will require clinic visits at screening, vorapaxar dosing day, 24 hours post initial vorapaxar dosing, 3-4 weeks post-dosing, 2 weeks post vorapaxar discontinuation, and 4 weeks post vorapaxar discontinuation. Patient instructions for the run-in phase will be given during the screening visit. One day prior to the run-in, the study coordinator will call the subject to remind subjects of run-in instructions.

A tabulated overview (Table 1) of the procedures conducted in each of these periods is provided in section 9.1 and the procedures and their timing are described in more detail in the remaining sections.

9.1 Tabulated overview

Table 1. Schedule of evaluations

	V1		V2	V3	V4	V5	V6/EOS
	Screening (28 days from V2)	Run-In* (Start 7 ± 3 days prior to scheduled V2)	Group 1: 3-28 days of screening Groups 2,3,4: 7-28 days of Screening	24 hours of 1 st study drug dose	30 +/- 7 days 1 st study drug dose	14 +/- 3 days of Visit 4	14 +/- 3 days of Visit 5
Informed Consent	X						
Inclusion/Exclusion Criteria	X						
Medical History	X						
Review Prior/Concomitant Medications	X	X#	X	X	X	X	X
Vital Signs	X		X	X	X	X	X
12 lead ECG	X						
Blood and Urine for Safety Labs (CBC,CMP,UA,hsCRP)	X=				X		X
Physical Examination	X				X		
Endo-PAT2000 Test			X		X		
PD/hsCRP/urine			X	X	X	X	X
Buccal Swab for CYP2C19*2 Testing	X						
Dispense Study Drug		X#	X		X#	X#	
Administer Vorapaxar			X				
ASA and/Clopidogrel Dairy Completion		X#	X				
Drug accountability			X	X	X	X#	X#
Adverse Events		X#	X	X	X	X	X

X Applies to all subjects for that visit

X# Applies only to subjects in groups 2, 3, and 4

X= Blood and Urine Safety Labs collection *only* for subjects with no lab results on record that are ≤ 30 days from screening visit

Screening and run-in visit can occur at the same day if the subject's medical records and safety laboratory results (should be ≤30 days from screening) are readily available for review. For these subjects, instructions should be given the day of screening/run-in visit to hold any standard home treatment of EC ASA and/or clopidogrel (if assigned to groups 2, 3, and 4). Schedule the screening/run-in visit 7+3 days from visit 2.

9.2 Timing of Assessments

9.2.1 Screening

Subjects will be contacted prior to screening visit to ensure that the subject is eligible for the study. The screening visit will take place within 28 days (to allow time for medical records and safety laboratory results collection and review) from the vorapaxar dosing day (visit 2).

Subjects with medical records and laboratory results (within 30 days), readily available for review, can undergo screening and run-in phase at the same visit (only if assigned to groups 2, 3, and 4). If this is the case, schedule the screening/run-in visit 7+3 days from visit 2. Subjects with a scheduled screening/run-in visit will be instructed by the study coordinator not to take their EC ASA and/or clopidogrel at home in the morning of scheduled visit. Subject will be given study EC ASA and/or clopidogrel at the research site. If medical records and lab results are not available at the screening visit, patients will be asked to return to site for run-in phase.

During the screening visit, the following will be completed and documented in the Case Report Forms (CRF):

- Obtain written informed consent
- Complete inclusion/exclusion criteria
- Obtain demographic information (i.e. date of birth, gender, and race)
- Record medical history (including medical history and smoking history)
- Record medication history
- Perform complete physical examination
- Obtain height and weight
- Obtain and record vital signs
- Buccal cell sample will be collected for CYP2C19*2 testing. The actual date and clock time of buccal sampling will be recorded in the CRF.
- Obtain clinical safety laboratory specimens/results comprehensive metabolic panel, complete blood count with platelets and auto differential, high sensitivity C-reactive protein) *Note: Laboratory results collected within 30 days of screening are allowed for review.*
- Obtain urine samples for urine analysis and urine thromboxane. *Note: Urinalysis results collected within 30 days of screening are allowed for review.*
- Obtain 12-lead ECG *Note: EKG results collected within 90 days of screening are allowed for review.*
- Provide patient education about medication intake:
 - Continue standard home treatment for EC aspirin and clopidogrel until next study visit (run-in or visit 2).
 - Subjects who are currently using any medications not approved by the Investigator will be excluded.
 - Avoid grapefruit or grapefruit juice during the study period.
 - If the subject's medical records and laboratory results are readily available for a thorough review by the investigator during the screening visit (i.e., able to access

medical records and laboratory results in INOVA EPIC system), the run-in phase can be completed at the same visit (see section 9.2.2)

- Schedule next visit. Once verified to be eligible for enrollment, subjects in group 1 will be scheduled for visit 2 and 3. Subjects belonging in groups 2, 3, and 4 will be scheduled for the run-in phase, visit 2, and 3. Subjects will be informed via phone call to confirm scheduled visits.

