3.1.1 Run-in

Eligible subjects (excluding subjects in group 1) who have signed informed consent will complete the run-in period. Subjects will be instructed to continue on their prescribed antiplatelet regimen, EC ASA and/or clopidogrel; however, the medications will be provided to the subjects by the study site for compliance accounting purposes. Study diaries will be provided for the run-in period only (7 -10 days) and pill reconciliation will be performed for all visits. The subjects will postpone taking their antiplatelet regimen in order to take the dose during this visit from the medication provided by the study site. Subjects will be assigned into the following groups:

- Subjects in group 2 will receive clopidogrel 75mg orally daily provided by the study site. Subjects in group 3 will receive EC ASA 81 mg orally daily provided by the study site.
- Subjects in group 4 will receive clopidogrel 75mg in addition to EC ASA 81mg orally daily provided by the study site.

Subjects will be grouped according to their current antiplatelet regimen. Subjects with cardiovascular risk factors not on antiplatelet therapy will be included in either Group 1 or 2. Patients on ASA alone will be included in Group 3 and patients on dual antiplatelet therapy will be in Group 4. All doses will be in tablet form for oral administration.

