4.8 Study Treatment/Intervention-

This phase IV, open label, pharmacodynamic investigation will be conducted in patients between 18-75 years of age with multiple coronary artery disease risk factors (antiplatelet naïve patients) and patients with prior MI or PAD on antiplatelet therapy (Figure 1). Informed consent will be obtained from subjects meeting the inclusion criteria before the initiation of any study-specific procedures. Subjects will be grouped according to their current antiplatelet regimen. Subjects with cardiovascular risk factors not on antiplatelet therapy will be included in either Group 1 or 2. Patients on ASA alone will be included in Group 3 and patients on dual antiplatelet therapy will be in Group 4.

- Group 1 (control group): vorapaxar 2.08mg orally once daily
- Group 2: clopidogrel 75mg orally once daily + vorapaxar 2.08mg orally once daily
- Group 3: EC aspirin 81mg orally once daily + vorapaxar 2.08mg orally once daily
- Group 4: EC aspirin 81mg orally once daily + clopidogrel 75mg orally once daily + vorapaxar 2.08mg orally once daily

The study comprises 6 periods: screening, run-in (for subjects in groups 2, 3, and 4), onset and maintenance, offset, and end of study (Figure 1). The trial will require clinic visits at screening, vorapaxar dosing day, 24 hours post initial vorapaxar dosing, 3-4 weeks post-dosing, 2 weeks post vorapaxar discontinuation, and 4 weeks post vorapaxar discontinuation. Patient instructions for the run-in phase will be given during the screening visit. One day prior to the run-in, the study coordinator will call the subject to remind subjects of run-in instructions.

Pharmacodynamics will be assessed at multiple time points to assess onset-, maintenance-, and offset-effect of vorapaxar on thrombin generation, platelet reactivity, and plasma/platelet endothelial and inflammatory biomarkers. Safety assessment will be assessed throughout the study. Approximately 25-30ml of blood will be drawn at each visit. Phlebotomy sites will be carefully chosen to minimize risk. See schedule of procedures in section 7 for detailed schedule of study events.

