4.9 Consent

Eligible subjects may only be included in the study after providing written (witnessed, where required by law or regulation), IRB/IEC/REB-approved informed consent, If the subject is capable of doing so, he/she should indicate assent by personally signing and dating the written informed consent document or a separate assent form. Informed consent must be obtained before conducting any study-specific procedures (i.e., all of the procedures described in the protocol). The process of obtaining informed consent should be documented in the subject source documents.

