8.6.1.3.9 Other potential adverse events

Other potential adverse events as related to subject's concomitant diseases. To prevent subjects from missing any medications while in-clinic, all subjects will be instructed to take all approved concomitant medications (i.e., insulin, anti-hypertensive medications) with them to be taken as allowed by study protocol. A small snack will also be provided to subjects after laboratory and endo-pat testing to prevent hypoglycemic episodes, especially for diabetic patients. Water will be allowed throughout each outpatient visits.

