9.2.2 Run-In Phase

Subjects in groups 2, 3, and 4 will undergo a run-in phase once deemed eligible for enrollment. The run-in phase will be started 7 + 3 days prior to a scheduled visit 2 (vorapaxar dosing day). Subjects will be informed via phone call, a day before, to hold their current home medication of clopidogrel and/or EC ASA the morning of scheduled run-in visit.

If the subject has medical records and safety laboratory test results readily available for review during the screening visit, the run-in phase can be completed at the same time as screening. Instruct subjects to hold home medication of clopidogrel and/or EC ASA the morning of scheduled screening/run-in visit. During this visit, the following procedures will be performed:

- Collection of adverse events.
- Collection of concomitant medications.
- Confirm continue eligibility.
- Administer first dose of study treatment. Document first dose of study treatment as specified below as day 1 of the run-in phase.
 - Group 2: Administer one dose of clopidogrel 75mg orally
 - Group 3: Administer one dose of EC ASA 81mg orally.
 - Group 4: Administer one dose of clopidogrel 75mg and EC ASA 81mg.
- Dispense study drug (EC ASA and/or clopidogrel) for subjects in groups 2, 3, and 4 only.
 - Group 2: 10 tablets of clopidogrel 75mg
 - Group 3: 10 tablets of EC ASA 81mg
 - Group 4: 10 tablets of clopidogrel 75 mg and EC ASA 81mg
- Provide patient education (for EC ASA and/or clopidogrel).
- Provide subject instructions.

To continue on their prescribed antiplatelet regimen, clopidogrel and/or EC ASA; however, the medications will be provided to the subjects by the study site with the following instructions::

 - Group 2 subjects: Take clopidogrel 75mg orally once a day starting the next day, preferably in the morning.
 - Group 3 subjects: Take EC ASA 81mg orally once a day starting the next day, preferably in the morning.
 - Group 4 subjects: Take clopidogrel 75mg and EC ASA 81mg orally once a day starting the next day, preferably in the morning.
- Provide study drug diary for all subjects. Document first dose of study treatment as day 1 of the run-in phase.

9.2.3 Visit 2

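### On the optional same-day screening/run-in route, Group 3 and 4 subjects hold their morning antiplatelet dose before written consent, and those who do not enter get no explicit instruction to take it

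*Combined protocol and SAP*

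**What the plan says.** **Consent.** Section 4.9 states: "Informed consent must be obtained before conducting any study-specific procedures (i.e., all of the procedures described in the protocol"). Section 4.8 says, in a sentence that also appears in Section 2.1: "Informed consent will be obtained from subjects meeting the inclusion criteria before the initiation of any study-specific procedures". Section 3.1.1 restricts run-in in the same way: "Eligible subjects (excluding subjects in group 1) who have signed informed consent will complete the run-in period". Table 1 shows informed consent at V1 only, and Section 9.2.1 lists it first among the tasks done during the screening visit.

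**The hold.** For subjects booked to screen and start run-in together, Section 9.2.1 says: "Subjects with a scheduled screening/run-in visit will be instructed by the study coordinator not to take their EC ASA and/or clopidogrel at home" on the morning of the visit. Section 9.2.2 repeats it: "Instruct subjects to hold home medication of clopidogrel and/or EC ASA the morning of scheduled screening/run-in visit". Section 3.1.1 gives the reason: "The subjects will postpone taking their antiplatelet regimen in order to take the dose during this visit", using tablets supplied by the site.

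**When the instruction is given.** The Table 1 note says that "instructions should be given the day of screening/run-in visit to hold any standard home treatment of EC ASA and/or clopidogrel". Sections 4.8 and 9 say that run-in instructions are given at screening, and that the coordinator telephones a reminder the day before run-in.

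**The replacement dose.** Sections 9.2.1 and 9.2.2 have it given on site as run-in Day 1. Section 9.2.2 reserves run-in for subjects already judged eligible.

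**The concern.** A patient with prior MI or PAD is asked to change the timing of a prescribed antiplatelet dose for the study's purposes before agreeing to take part. The protocol's own rule is consent first. The replacement dose belongs to run-in, so someone who attends, having held the dose, and then declines or proves ineligible falls outside the step that would make it good. What is at stake is subject protection and consistency within the protocol. No estimate or test depends on it.

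**Working it through.** There is no stated figure to reproduce. The check compares sections, with some counting.

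**1. Order of events on the same-day route.**
- Morning, at home: dose not taken (9.2.1, 9.2.2).
- At the visit: written consent, then eligibility review (9.2.1, Table 1).
- Still at the visit, if eligible: study-supplied dose (9.2.1, 9.2.2).

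The hold comes before consent. The day-before reminder call (4.8, 9) does too, because on this route the day before run-in is also the day before screening. On the ordinary two-visit route the hold call follows screening and consent, so those subjects are not affected.

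**2. Who has a home dose to hold.** Sections 3.1.1 and 4.8 place subjects not on antiplatelet therapy in Groups 1 and 2. Only Groups 3 and 4 have a home dose: 25 + 25 = 50 of 100 planned subjects. The route is optional and its share is not stated, so the count of enrolled subjects runs from 0 to 50.

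**3. Dependence on genotyping.** Section 4.7 requires a CYP2C19 swab at screening for the clopidogrel groups, makes \*2/\*2 a screen failure, and gives no turnaround time. Assumption: if the result is not available the same day, Group 4 could not be cleared to start run-in at that visit and would not be booked this way. The upper limit is then about 25 (Group 3 alone).

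**4. What covers the held dose, by outcome of the visit.**

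| Outcome | Covering text |
|---|---|
| Consents and enters run-in | On-site dose (9.2.1, 9.2.2) |
| Consents, records missing, deferred | Partial: screening education in 9.2.1 to keep taking home treatment until the next study visit |
| Consents, fails screening | Possibly the same education, though it is worded for people with a next visit |
| Declines | None explicit |

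The missed-dose rule in Section 3.2 concerns study treatment only. The Section 9.2.3 instruction to bring home medicines and take them after testing is for Visit 2.

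**5. Endpoints.** Baseline PD is drawn at Visit 2. With the 7 + 3 day booking in Section 9.2.1 and the Table 1 note, that is at least 7 days after a same-day visit. Section 9.2.1 does collect urine thromboxane at screening, but Section 5.2 names no endpoint based on it.

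**6. Would starting run-in the next morning fit?** A visit *d* days before Visit 2 puts Day 1 at *d* − 1 days before.
- *d* = 8, 9, 10 gives Day 1 at 7, 8, 9 days: inside 7 + 3 (9.2.1, 9.2.2) and inside the 7–10 day run-in of Section 3.1.1.
- *d* = 7 gives Day 1 at 6 days and only 6 doses before Visit 2. The 7 ± 3 window in the Table 1 header allows this, but the 7–10 days in Section 3.1.1 do not.
- Bookable days fall from 4 (7–10) to 3 (8–10).
- Doses before Visit 2 are 7 to 9, or 8 to 10 counting the Visit 2 dose, within the 10 tablets dispensed.

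**The case against.** **The timing is not settled.** The Table 1 note and the statement in Sections 4.8 and 9 that run-in instructions are given at screening both fit an instruction given on arrival. That is a fair reading of those places, and the sections need aligning. It does not remove the point: none of them makes the hold conditional on consent, and Section 9.2.1 has the dose withheld at home.

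**The hold may not be a procedure.** It is neither a row of Table 1 nor an item in the Section 9.2.2 list, and taking a daily tablet some hours late is a small thing. This is a matter of interpretation. But Section 4.9 defines the term broadly, and Section 3.1.1 shows that the postponement exists only so that study supply can be used.

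**Other text protects the subject.** Section 8.6.1.3.9 says: "To prevent subjects from missing any medications while in-clinic, all subjects will be instructed to take all approved concomitant medications" with them. Its examples are insulin and anti-hypertensives, and use is subject to the protocol, so it does not plainly reach the held antiplatelet. More weight goes to the fact that the hold covers only the dose at home that morning. Nothing forbids taking it later, and nothing suspends the existing prescription.

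**Stronger readings that the documents do not support.** A reader might infer that patients are left without antiplatelet therapy. Entrants are dosed the same day, and others lose at most one dose. A reader might infer that nobody outside run-in has any cover. The home-treatment education in Section 9.2.1 reaches deferred subjects and may reach some consented screen failures. A reader might take 50 as a firm cap. It assumes a same-day genotype for Group 4.

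**Conclusion.** The point stands as a minor one. As written, the same-day route has Group 3 and 4 subjects hold a prescribed dose before consent, contrary to Sections 2.1, 4.8 and 4.9 if the hold counts as a study-specific procedure, which is the natural reading of Section 4.9.

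Between 0 and 50 enrolled subjects are affected, with an upper limit of about 25 on the genotyping assumption, and each has one dose postponed by hours. Only those who take their dose in the morning are concerned. People who decline, and probably those who fail screening that day, come on top of this. The documents give no rate for them, so no count is offered. For each, the consequence is at most one delayed or missed daily dose. No analysis or endpoint is touched.

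**What to change.** In Sections 9.2.1 and 9.2.2 and the Table 1 note, permit the hold only after signed consent. There are two ways to do this:

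- **Consent earlier.** Obtain IRB-approved consent before the hold call. This keeps the on-site first dose. The cost is an additional consent step before the visit.
- **Start run-in the next morning.** Same-day Group 3 and 4 subjects take the home dose as usual, are consented, screened and given study supply, and begin Day 1 the following day. Book the visit 8–10 days before Visit 2. The cost is the site-observed first run-in dose and one booking day. Group 2 keeps its on-site Day 1.

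In either case add one sentence to Section 9.2.1: *Anyone who held the home dose and does not start run-in that day takes the usual dose before leaving.* This is a wording change only. Also align the timing statements in Sections 4.8 and 9 and the Table 1 note with Sections 9.2.1 and 9.2.2, so that all say when the instruction is given.

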2.5 Inclusion Criteria

The study will include subjects who have multiple risk factors of developing atherosclerosis or evidence or a history of atherosclerosis involving the coronary or peripheral vascular systems. Subjects may be enrolled if they appropriately fulfill all inclusion criteria and none of the exclusion criteria.

Inclusion Criteria: Subjects must meet ALL the criteria listed below for entry:

1. Subject may be of either sex and of any race, and must be between 18 and 75 years of age.
2. Subject must have multiple risk factors of developing atherosclerosis, or evidence of a history of atherosclerosis involving the coronary or peripheral arterial systems as follows:
 - a. Subject must present with multiple risk factors for CAD or PAD such as high blood pressure, high cholesterol, diabetes, obesity, current smokers, 55 years or older, or
 - b. CAD as indicated by a history of presumed spontaneous MI (hospitalized with final diagnosis of MI, excluding periprocedural or definite secondary MI due to profound anemia or hypertensive emergency or troponin increase in sepsis) at least 1 month prior to enrollment, or
 - c. PAD as indicated by a history of intermittent claudication and
 - i. a resting ankle/brachial index (ABI) of <0.85 , or

- ii. significant peripheral artery stenosis (>50%) documented by angiography or non-invasive testing by duplex ultrasound, or
 - iii. previous limb or foot amputation for arterial vascular disease (excludes trauma), or
 - iv. previous aorto-femoral bypass surgery, limb bypass surgery or percutaneous transluminal angioplasty of the iliac or infrainguinal arteries.
3. Subject must be willing and able to give appropriate informed consent.
 4. The subject is able to read and has signed and dated the informed consent document including authorization permitting release of personal health information approved by the investigator's Institutional Review Board (IRB).

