2.6 Exclusion Criteria

Exclusion Criteria: Subjects will be excluded from entry if ANY of the criteria listed below are met:

1. Clinically unstable at the time of enrollment.
2. Any planned coronary revascularization or peripheral intervention.
3. Concurrent or anticipated treatment with warfarin (or derivatives, e.g., phenprocoumon), oral factor Xa inhibitor, or oral direct thrombin inhibitor after enrollment.
4. Concurrent or anticipated treatment with a potent inducer (e.g., rifampin) or potent inhibitor (e.g., ketoconazole, erythromycin) of CYP3A4 isoenzymes (see Appendix B) (but see note in text for exceptions).
5. History of a bleeding, or evidence of active abnormal bleeding.
6. History at any time of intracranial hemorrhage, intracranial or spinal cord surgery, or a central nervous system tumor or aneurysm.
7. Documented sustained severe hypertension (systolic blood pressure >200 mmHg or diastolic blood pressure >110 mmHg) at enrollment or within the previous 10 days.
8. Severe valvular heart disease, as defined by the American College of Cardiology /American Heart Association.
9. History within 30 days before enrollment of invasive surgeries (other than mentioned above), or is anticipating one during the course of their study participation, or is planning to have one within 1 month post dosing with the study drug.
10. History within 30 days before enrollment of TIA and ischemic (presumed thrombotic) stroke/CVA.
11. Known platelet count <100,000/mm³ within 30 days before enrollment.
12. Known active hepatobiliary disease, or known unexplained persistent increase in serum alanine aminotransferase (ALT) or aspartate aminotransferase (AST) activity to two times or more the upper limit of the reference range (upper limit of "normal" [$\uparrow 2 \times \text{ULN}$]).
13. Any serious illness or any condition that the investigator feels would (a) pose a significant hazard to the subject if investigational therapy were initiated, or (b) would limit the prognosis of the subject, regardless of investigational therapy.
14. Any serious medical comorbidity (e.g., active malignancy) such that the subject's life expectancy is <24 months.
15. Known current substance abuse at the time of enrollment.
16. Current participation in any other study of investigational therapy or participation in such a study within the last 30 days.
17. Known hypersensitivity to any component of the current investigational product.
18. Female subject of child-bearing potential.

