The study coordinator will call the eligible subjects the day before to review protocol instructions and study related activities for Visit 2 and answer any potential questions. Remind the subjects to hold their clopidogrel and/or EC ASA (study medications) and all other medications taken by the subjects regularly. Subjects will be instructed to bring all home medications with them for the appointment to take after the bloodwork and testing. Ask subjects to avoid any high fat foods the morning of the visit. For the Endo-PAT2000 test, the subject needs to abstain from smoking and caffeine 2 hours prior to testing. Subjects also need to hold any vasoactive medications 24 hours prior to the test.

The dosing visit will occur within 3 to 28 days of screening for subjects in group 1. Visit 2 for groups 2, 3, and 4 will occur within 7 + 3 days from the run-in period.

During this visit, the following procedures will be performed:

- Vital signs (blood pressure, heart rate) will be obtained after the subject has been in a sitting position for at least 5 minutes.
- Collection of Study Drug Diary for subjects in groups 2, 3, and 4.
- Study drug accountability will be performed (groups 2, 3, and 4).
- Administer Endo-PAT2000 test.
- Blood and urine samples will be obtained for baseline PD measurements through direct venipuncture. The actual date and clock time of blood/urine sampling will be recorded in the CRF.
- Provide a small snack after blood and urine specimen collection
- If applicable, after lab work collection and endo-PAT2000 test, remind subject to take approved home medications as according to subject's regular schedule. Subjects will receive first dose of vorapaxar 2.08mg orally. After administering first dose of vorapaxar, administer daily dose of study treatment (clopidogrel and/or EC ASA) to subjects as according to assigned group (to prevent a missing dose).
- Subject will return to clinic in 2 hours (+ 60 mins) post vorapaxar dosing time for PD blood draw.
- Collection of adverse events.
- Collection of concomitant medications.
- Dispense study drugs
 - Group 1: A bottle of 37 tablets of vorapaxar 2.08mg
 - Group 2: A bottle of 37 tablets of vorapaxar 2.08mg and 37 tablets of clopidogrel 75mg
 - Group 3: A bottle of 37 tablets of vorapaxar 2.08mg and 37 tablets of EC ASA 81mg.
 - Group 4: A bottle of 37 tablets of vorapaxar 2.08mg, 37 tablets EC ASA 81mg, and 37 tablets of clopidogrel 75mg.
- Provide patient education for vorapaxar

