17 APPENDICES

17.1 Appendix A: Bleeding Academic Research Consortium (BARC) definition for Bleeding

Type 0
 
 No bleeding

Type 1
 
 Bleeding that is not actionable and does not cause the patient to seek unscheduled performance of studies, hospitalization, or treatment by a health-care professional; may include episodes leading to self-discontinuation of medical therapy by the patient without consulting a health-care professional.

Type 2
 
 Any overt, actionable sign of hemorrhage (e.g., more bleeding than would be expected for a clinical circumstance, including bleeding found by imaging alone) that does not fit the criteria for type 3, 4, or 5 but does meet at least one of the following criteria: 
 requiring nonsurgical, medical intervention by a health-care professional, leading to hospitalization or increased level of care, or prompting evaluation

Type 3
 
 Type 3a: 
 Overt bleeding plus hemoglobin drop of 3 to < 5 g/dL* (provided hemoglobin drop is related to bleed) Any transfusion with overt bleeding Type 3b: 
 Overt bleeding plus hemoglobin drop ≥ 5 g/dL* (provided hemoglobin drop is related to bleed), Cardiac tamponade, Bleeding requiring surgical intervention for control (excluding dental/nasal/skin/hemorrhoid), Bleeding requiring intravenous vasoactive agents Type 3c: 
 Intracranial hemorrhage (does not include microbleeds or hemorrhagic transformation, does include intraspinal), Subcategories confirmed by autopsy or imaging or lumbar puncture, Intraocular bleed compromising vision.

Type 4
 
 CABG-related bleeding, Perioperative intracranial bleeding within 48 h, Reoperation after closure of sternotomy for the purpose of controlling bleeding Transfusion of ≥ 5 U whole blood or packed red blood cells within a 48-h period, Chest tube output more than or equal to 2L within a 24-h period

Type 5 (Fatal bleeding)
 
 Type 5a: Probable fatal bleeding; no autopsy or imaging confirmation but clinically suspicious

- **Type 5b:** Definite fatal bleeding; overt bleeding or autopsy or imaging confirmation

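### Safety labs are dated from screening, so the only scheduled platelet count and hemoglobin before vorapaxar can be up to 58 days old, and exclusion 11 counts from an undefined enrollment date

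*Combined protocol and SAP*

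**What the plan says.** Section 9.2.1 lets existing safety labs stand in for a new draw: "Laboratory results collected within 30 days of screening are allowed for review". The X= footnote to Table 1 (section 9.1) agrees. A screening draw is taken only "for subjects with no lab results on record that are ≤ 30 days from screening visit".

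Section 9.2.1 also places screening relative to vorapaxar dosing: "The screening visit will take place within 28 days" of Visit 2. For Group 1, section 9.2.3 says "The dosing visit will occur within 3 to 28 days of screening for subjects in group 1". Table 1 gives 7 to 28 days for Groups 2 to 4.

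Table 1 has no safety-lab entry at run-in or Visit 2. The procedure lists agree: section 9.2.2 has no blood draw, and section 9.2.3 has only pharmacodynamic blood and urine samples before the first vorapaxar dose.

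Exclusion 11 (section 2.6) counts from a different point: "Known platelet count <100,000/mm³ within 30 days before enrollment". No section defines enrollment. Sections 9.2.1 and 9.2.2 speak of subjects being found eligible for it before the next visits are scheduled or run-in starts, which suggests an order of steps but gives no date.

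**The concern.** The age limit on accepted labs runs back from screening, while the exposure of interest begins up to four weeks later. A platelet count that looks recent at screening can be about two months old when vorapaxar starts. Section 8.6.1.3.1 describes vorapaxar as raising bleeding risk, including intracranial and fatal bleeding, and section 8.8.6.1 says its antiplatelet effect has no known reversal.

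Two things are at stake:

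- **Eligibility.** The look-back for accepted labs and the window in exclusion 11 have different anchors, one of them undefined. Two people auditing the same platelet result could reach different answers.
- **Safety baseline.** The same draw supplies the only scheduled hemoglobin before vorapaxar. Bleeding is to be documented by the BARC scale, and one type 3a criterion is "Overt bleeding plus hemoglobin drop of 3 to < 5 g/dL* (provided hemoglobin drop is related to bleed"). A drop needs a reference value, and here that value may be old.

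**Working it through.** The protocol states no maximum lab age at dosing, so there is no figure of its own to reproduce. The check adds its own windows.

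**Inputs**
- Maximum lab age at screening: 30 days (9.2.1; Table 1 footnote).
- Maximum gap from screening to Visit 2: 28 days (9.2.1; Table 1; 9.2.3 for Group 1).
- Same-day screening and run-in, Groups 2 to 4: 7 + 3 days before Visit 2, so at most 10 (9.1, 9.2.1).
- Start of a separate run-in: 7 + 3 days before Visit 2 in 9.2.2, but 7 ± 3 in the Table 1 column heading. The latest start is therefore 7 or 4 days before Visit 2.

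**Lab age at first vorapaxar dose** = lab age at screening + gap from screening to Visit 2
- Group 1, or Groups 2 to 4 with a separate run-in: 30 + 28 = 58 days.
- Groups 2 to 4, same-day screening and run-in: 30 + 10 = 40 days.
- Result already 30 days old at screening, shortest Group 1 gap: 30 + 3 = 33 days.
- Fresh draw at screening, longest gap: 0 + 28 = 28 days.

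**Maximum lab age at enrollment**, by what enrollment might mean

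| Enrollment taken as | Arithmetic | Maximum lab age | Agrees with 30 days in exclusion 11? |
|---|---|---|---|
| Screening visit | 30 + 0 | 30 days | Yes |
| Start of separate run-in (7 + 3) | 30 + 28 − 7 | 51 days | No |
| Start of separate run-in (7 ± 3) | 30 + 28 − 4 | 54 days | No |
| Visit 2 | 30 + 28 | 58 days | No |

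**Does another provision close the gap?**
- Section 3.1.2 has lab results confirmed before Group 1 receives vorapaxar, but sets no age limit.
- Section 9.2.2 asks for continued eligibility to be confirmed at run-in, with no lab attached. Group 1 has no run-in.
- Section 8.4 removes subjects who meet an exclusion after screening, but no scheduled CBC before dosing would reveal it.
- Figure 1 (section 2.1) lists safety labs at 24 hours, which Table 1 and section 9.2.4 omit. That inconsistency needs reconciling, but those labs would come after the first dose and do not shorten the pre-dose gap.

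**The case against.** The strongest reply is that no contradiction with exclusion 11 has been shown. That criterion bars a known low count in a period before enrollment. It does not require any count within 30 days of vorapaxar. Table 1 completes the eligibility criteria at Visit 1 only, and if enrollment is that visit the two windows are identical. This stands: a reader might infer that the protocol breaks its own exclusion, but the text supports only a conditional conflict.

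Second, 58 days is a corner case, reached only when an on-record result at the limit meets the longest screening gap. The protocol does not say how many of the 100 subjects would rely on existing results. This also stands, and the figure should be read as a maximum.

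Third, the hemoglobin argument is partly inference. No section says which hemoglobin anchors a BARC drop, types 3a and 3b can be met without one, and the endpoints in section 5.2 include no bleeding analysis. That limits the point to the quality of the safety baseline. It does not change the fact that no later pre-dose value is scheduled.

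Fourth, investigator review and unscheduled tests offer some protection. They do, but none requires a dated CBC before dosing.

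**Conclusion.** The point holds in a limited form. As scheduled, vorapaxar can start on a platelet count and hemoglobin up to 58 days old (40 days with same-day screening and run-in). This assumes that an on-record result is accepted at its limit, that the longest permitted gap is used, and that no unscheduled test is done. Whether this also conflicts with exclusion 11 depends on the missing definition of enrollment. It concerns platelets only, since no eligibility criterion concerns hemoglobin.

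Four wider readings are not supported:

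- **Liver exclusion cleared on stale values.** Exclusion 12 has no time window and concerns known disease or persistent elevation.
- **Labs from an infarction admission as baseline.** The infarction must be "at least 1 month prior to enrollment, or" so the overlap again turns on the undefined date. If enrollment is screening, it shrinks to a boundary day or a prolonged admission.
- **Group 2 labs predating clopidogrel.** A screening baseline precedes run-in by design, and a fresh screening draw would too.
- **A 95-day interval between CBCs** (58 + 37, to the latest Visit 4). This follows Table 1 alone. With the 24-hour labs in Figure 1 the interval would be about 58 + 1 = 59 days.

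The remaining point is a modest, inexpensive improvement to patient safety and baseline quality.

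**What to change.** Define enrollment as a dated event. Then reconcile exclusion 11 (2.6), the Table 1 footnote (9.1) and section 9.2.1 so that the look-back for accepted CBC and CMP results has one anchor tied to the start of study drug. The text should say whether that means the run-in drugs or vorapaxar. The length of the window is for the sponsor and investigator to choose.

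Where an on-record result would fall outside the reconciled window, either:

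- take the screening draw Table 1 already provides for, which is at most 28 days old at Visit 2; or
- add a CBC/CMP tube to the pre-dose Visit 2 venipuncture and name it as the safety baseline. It can inform eligibility only if the result is read before dosing.

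Do not narrow exclusion 11 in the process. For example, a low count drawn 25 days before screening, with Visit 2 held 20 days after screening, is 25 + 20 = 45 days old at dosing. Counting 30 days back from Visit 2 would drop that known low count from the exclusion.

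Reconcile Figure 1 with Table 1 on the 24-hour safety labs at the same time.

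The cost is wording in a few places and extra CBC/CMP tests for some subjects. To illustrate the burden without recommending a window: if 30 days were counted back from Visit 2 and the gap were 28 days, only results at most 30 − 28 = 2 days old at screening could be reused. Visit 2 may be scheduled after the screening draw is decided, and Group 1 has no visit in between. The Visit 2 tube is then the option that needs no extra visit.
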